Please note, that per NCCN guidelines for treatment of ER positive breast cancer, Goserelin acetate (Zoladex) (3.6 mg subcutaneous every 28 days) will be given per SOC practice to pre-menopausal and peri-menopausal women. This is standard of care for the treatment of pre- and peri- menopausal women and is not considered part of the study. The metabolism of goserelin is not CYP-mediated; rather hydrolysis of C-terminal amino acids is the major clearance mechanism. Based on the available information, goserelin is not expected to affect the metabolism of ribociclib nor be affected by co-administered drugs.

Safety Evaluation

Toxicity assessment, interim history and physical exam, CBC and chemistry profile weekly in cycle 1, then at day 1 of each cycle thereafter. Adverse Events and other symptoms will be assessed continuously and graded according to the NCI Common Toxicity Criteria, (CTCAE) v.4. Patients will be followed for evaluation of safety for at least 30 days after the last dose of study drug or until resolution of the AE. Any study drug-related serious adverse events will be followed until resolution, return to baseline grade, or deemed irreversible by the investigator.

Dose and Treatment Schedule

No of pts	Cohort Level	Ribociclib	Tamoxifen
3-6 (phase 1)	1	400 mg oral days 1-21, followed by 1 week break	20mg oral daily
3-6 (phase 1)	2	400 mg continuous	20 mg oral daily
3-6 (phase 1)	3	600 mg oral day 1-21 followed by 1 week break	20 mg oral daily

15 (dose expansion)	Phase Ib dose expansion	600 mg oral day 1-21 followed by 1 week break	20 mg oral daily
15 (dose expansion)	Phase Ib –dose continuous dosing cohort	400 mg oral daily	20 mg oral daily

* Goserelin acetate (Zoladex) 3.6 mg subcutaneous every 28 days will be given per NCCN guideline to pre-menopausal and peri-menopausal patients as described above. We will define this further in the full protocol.

* If the daily dosing is too bone marrow suppressive, then this arm will switch to 400 mg oral days 1-21, followed by 1 week break of a 28 day cycle.

Prohibited Medications:

- No other chemotherapy, hormonal therapy, radiotherapy, or experimental anticancer medications for the primary disease will be permitted while the patient is on study.
- Strong inhibitors or inducers of CYP3A4/5
- Substrates of CYP3A4/5 with narrow therapeutic windows
- Medications that carry a strong risk for QT prolongation
- Herbal medications/preparations not prescribed by treating MD

Statistical Considerations

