The **secondary objective** is to evaluate 2 dose expansion cohorts after the maximum-tolerated dose (MTD) has been reached to better characterize the toxicity profile and identify early signs of efficacy. Our goal is to assess the anti-tumor activity Ribociclib + Tamoxifen and to further evaluate their safety in adult patients with HR+/HER2- locally advanced or metastatic breast cancer.

To determine whether treatment with ribociclib improves response rate (RR) compared to the historical response rate with treatment with Tamoxifen alone. We know that the expected RR for Tamoxifen after failure of first line AI is about 10 % and therefore we hypothesize an improvement of RR to 25%.

Efficacy Evaluation

Response and progression will be evaluated in this study using the new international criteria proposed by the Response Evaluation Criteria in Solid Tumors (RECIST 1.1). This will be expanded in protocol.

DEFINITIONS:

DLT – Dose-Limiting Toxicity

MTD – Maximum tolerated dose

PFS – Progression-Free Survival

DDI – Drug-Drug Interaction

ER – Estrogen Receptor

PR – Progesterone Receptor

HER2 – Human Epithelial Receptor 2

PO – by mouth (per orum)

SERMS (selective estrogen receptor modulators)

SOC – standard of care

RR- Response Rate

FIH – First in human

Protocol:

The TEEL Study: A Phase I trial of Tamoxifen with Ribociclib (LEE011) in adult patients with advanced ER+ (HER2 negative) breast cancer.

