1 BACKGROUND AND RATIONALE

1.1 Introduction

Breast cancer is one of the most common cancers in the Western Hemisphere and the second most common cause of cancer deaths in women. Endocrine therapy, including ovarian ablation; estrogen; and, more recently, antiestrogen administration, has been a major component of antitumor therapy in breast cancer for more than a century. Hormone sensitive metastatic breast cancer remains a therapeutic challenge despite the many recent advances in therapy. Barring a few exceptions, cure is not achieved in this disease. While hormonal interventions have clearly shown to decrease the tumor burden and to prolong life, the majority of patients eventually recurs and succumbs to their disease.

More than two thirds of all the advanced breast cancers are dependent on estrogen. Estrogen-withdrawal by physical removal of the ovaries or inhibition of their function has been one of the earliest successful interventions against breast cancer; however this intervention was limited to premenopausal women. The introduction of the SERMS (selective estrogen receptor modulators) has dramatically improved the survival of women with breast cancer, both pre and postmenopausal. The most prominent SERM is Tamoxifen, which until recently has been the gold standard for first-line therapy for women with advanced hormone-sensitive breast cancer. The introductions of several aromatase inhibitors (AIs) have added greatly to the arsenal against breast cancer and have replaced Tamoxifen as first-line therapy. The production of estrogen in postmenopausal women requires an enzyme called aromatase. This aromatase enzyme has been successfully blocked chemically. The most commonly used aromatase inhibitors include letrozole, anastrozole and exemestane.

However, the AIs are reserved for women who have naturally entered menopause or have their ovarian function suppressed. For premenopausal women or women who are unable to tolerate AIs, Tamoxifen remains the gold standard. In addition to that, there are many postmenopausal women who cannot tolerate the side effect profile of Aromatase Inhibitors. The response rate to first line hormonal therapy determined from four pivotal randomized Phase III trials ranges from 20-33% (1, 5, 6, 10). The response

rate to second line hormonal therapy is considerably less (10-20%) (6), suggesting a clear need for more effective therapy.

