8 TREATMENT PLAN

Phase I/ Phase Ib dose expansion:

TAMOXIFEN: 20 mg PO daily will be given with RIBOCICLIB:

Ribociclib (LEE011)

In phase I: Ribociclib PO starting at a dose of 400 mg po for 21 days of a 28-day treatment cycle; this will be increased to 400 mg continuously. We will then evaluate 600 mg po daily for 21 days of a 28 day cycle if tolerated.

If there are no dose limiting toxicities, in the phase I portion, Tamoxifen 20 mg will be given with the MTD dose of Ribociclib in 15 patients. This is expected to be 600mg three weeks on and one week off. These patients will *not be stratified* for menopausal status.

If the 400mg continuous dose was well tolerated in the escalation arm, we will then expand this cohort in the phase Ib expansion, we will have an additional cohort of Tamoxifen 20 mg with 400 mg ribociclib in a continuous daily dose in an additional 15 patients. These patients will *not be stratified* for menopausal status.

Goserelin acetate (Zoladex) (3.6 mg subcutaneous every 28 days) will be given per NCCN guidelines to pre-menopausal and peri-menopausal. This will be given on day 1 of every cycle. We estimate that up to 20 of 40 patients on this protocol will require goserelin.

Goserelin is given if patient is premenopausal or peri-menopausal at the time of study entry.

Premenopausal status is defined as either:

- Patient had last menstrual period within the last 12 months.
- In case of therapy induced amenorrhea, with a plasma estradiol ≥ 10 pg/mL and/or FSH ≤ 40 IU/l or in the premenopausal range according to central laboratory definition.
- Patients who have undergone bilateral oophorectomy do not need goserelin.

Peri-menopausal status is defined as neither premenopausal nor postmenopausal (see exclusion criteria for definition).

8.1 Study Design:

Dose and Treatment Schedule – Table 8-1

No of pts	Cohort Level	RIBOCICLIB	Tamoxifen
3-6 (phase 1)	1	400 mg oral days 1-21, followed by 1 week break	20mg oral daily
3 -6 (phase 1)	2	400mg continuous	20 mg oral daily
3 -6 (phase 1)	3	600 mg oral day 1-21 followed by 1 week break	20 mg oral daily
15 (Ib dose expansion)	Phase Ib dose expansion	600 mg oral day 1-21 followed by 1 week break	20mg oral daily
15 (Ib dose	Phase Ib dose expansion-	400 mg oral daily	20 mg oral daily

expansion	continuous cohort	
------------------	--------------------------	--

Ribociclib Capsules/tablets for oral use 400 mg OR 600 mg Days 1-21 of each 28 day cycle or daily.

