10.2 Statistical Considerations for Phase Ib Dose expansion Study

If no MTD is observed with Level 1 through 3, we plan to continue/conduct the phase Ib dose expansion study as below. This expansion study is planned to understand and obtain initial efficacy data for the secondary endpoints.

Since the identical patient inclusion/exclusion criteria will be used in phase Ib dose expansion, all patient data from phase I dose escalation and phase Ib dose expansion studies can be combined for our statistical analysis, therefore, the required sample size of patients below will be both for phase I dose escalation and phase Ib dose expansion studies.

We obtained our statistical power and required sample size as a single-arm prospective study. In particular, for our evaluation of early efficacy we designed the study particular, for our evaluation of early efficacy we designed the study for testing $H_0: P \leq 0.10$ versus $H_1: P \geq 0.25$ at one-sided significance level 0.05 and power 0.80 as below.

P0	P1	Alpha	Beta	Cut-Off		Actual	Actual
				R + 1	N		
0.100	0.250	0.050	0.200	8	40	0.042	0.182

Where P0 is the maximum response proportion of standard care (tamoxifen alone), P1 is the minimum response proportion of our experimental treatment group, and N is the sample size.

For our statistical testing, if the number of responses $\geq R+1$, P0 is rejected based on Fisher's Exact test (34, 35). Alpha is the probability of rejecting that $P \leq P_0$ when this is true.

Beta is the probability of rejecting that $P \geq P_1$ when this is true.

Thus, the study requires 6 subjects under phase I dose escalation and 30 subjects under phase Ib dose expansion who will be treated with ribociclib (total 36) in order to test whether the proportion responding, P, is less than or equal to 0.100 or greater than or equal to 0.25. If the number of responses is 8 or more, the hypothesis that $P \leq 0.100$ is rejected with a target Type I error rate, α , of 0.050 and an actual error rate of 0.045. The null hypothesis will be rejected if 8 or more responses are observed in 40 patients. This design yields a type I error rate of 0.045 and power of 0.818 when the true response rate is 0.25.

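### Pooled response is tested against a tamoxifen-alone rate although about half the patients will also receive goserelin, so a positive result does not isolate a ribociclib effect

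*Combined protocol and SAP*

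**What the plan says.** **Comparator.** Section 10.2 defines P0 = 0.10 as the "maximum response proportion of standard care (tamoxifen alone"). The Synopsis (Statistical Considerations) asks whether ribociclib "improves response rate (RR) compared to the historical response rate with treatment with Tamoxifen alone". It sources the null, "We know that the expected RR for Tamoxifen after failure of first line AI is about 10" per cent, and the alternative, "therefore we hypothesize an improvement of RR to 25" per cent.

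**Test.** The design is single-arm, "at one-sided significance level 0.05 and power 0.80 as below". The null is rejected at 8 or more responses in 40. Escalation and expansion patients are combined.

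**Goserelin.** The Synopsis and section 2.5 plan goserelin for every woman who is not postmenopausal, estimated at approximately 20 of 40. Section 8 puts it as a ceiling: "We estimate that up to 20 of 40 patients on this protocol will require goserelin". It is scheduled on day 1 of each cycle. The Synopsis calls it standard of care for pre- and peri-menopausal women and says it "is not considered part of the study", while section 2 lists it among the treatments the study includes.

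**Grouping.** The Synopsis and section 8 state that there is no stratification by menopausal status. The Synopsis evaluates pre-menopausal women, post-menopausal women and men together. No analysis of response by menopausal status or goserelin use appears anywhere.

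**The concern.** The reference rate describes one background treatment, and about half the sample will receive another. If standard care for pre- and peri-menopausal women includes goserelin, as the Synopsis says, then equating standard care with tamoxifen alone is wrong for those patients.

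The protocol also regards ovarian suppression as active treatment. Section 1.1 says of the ovaries that "inhibition of their function has been one of the earliest successful interventions against breast cancer". Placing goserelin outside the study does not take its effect out of the response count. Any response it produces counts towards the 8 needed, and under the stated aim would be read as a gain from ribociclib.

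This is a co-treatment problem. A null rate matched to patients' prior therapy would still leave these patients on an agent that the reference lacks.

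**Working it through.** **Inputs from the documents:** P0 = 0.10, P1 = 0.25, N = 40, reject at 8 or more (section 10.2); about 20, or up to 20, of 40 on goserelin (Synopsis, sections 2.5 and 8).

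**Input not in the documents:** the response rate for tamoxifen plus goserelin without ribociclib, called p_g. It is assumed here and shown as a range.

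**Step 1. Reproduce the plan's figures.** With X ~ Bin(40, p):
- P(X ≥ 8 | p = 0.10) = 0.0419, matching the table's 0.042.
- P(X ≥ 8 | p = 0.25) = 0.8180, matching 1 − 0.182 = 0.818.

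The type I error of 0.045 in the text of section 10.2 does not reproduce at N = 40. That is a separate point; 0.042 is used below.

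**Step 2. Let the background differ, with ribociclib inert.** If m patients receive goserelin, X = X1 + X2, where X1 ~ Bin(40 − m, 0.10) and X2 ~ Bin(m, p_g) are independent. P(X ≥ 8) comes from the exact convolution of the two distributions.

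| Assumed p_g | m = 20 | m = 15 | m = 10 |
|---|---|---|---|
| 0.10 | 0.042 | 0.042 | 0.042 |
| 0.15 | 0.118 | 0.095 | 0.074 |
| 0.20 | 0.242 | 0.174 | 0.117 |
| 0.25 | 0.400 | 0.278 | 0.172 |

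With m = 20 the pooled no-effect rate is 0.5 × 0.10 + 0.5 × p_g, that is 0.125, 0.150 or 0.175 for the last three rows. Expected responses are 40 times this: 5, 6 or 7, against 4 under the plan's null.

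**Step 3. Where the assumed range sits.** Section 1.1 gives response rates of 10-20% for second-line and 20-33% for first-line hormonal therapy. The assumed 15-25% lies within that span. Those ranges differ by line of therapy, not by goserelin, so they show only that the values are not outlandish. They do not estimate p_g.

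**Step 4. What a split could deliver.** In a stratum of 20 tested against 0.10, the smallest cut-off holding one-sided 0.05 is 5: P(X ≥ 5 | 0.10) = 0.043 and P(X ≥ 5 | 0.25) = 0.585. Exact 95% intervals are wide: 5 of 20 gives 0.087 to 0.491, and 2 of 20 gives 0.012 to 0.317.

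**The case against.** The strongest reply is that nothing in the documents shows goserelin adding objective response to tamoxifen in metastatic disease. The remark in section 1.1 is historical. The goserelin study described in the Synopsis and section 2.5 is a retrospective survival comparison with chemotherapy in stage Ia to IIIa disease. This stands: the inflated figures rest on assumed rates, and at p_g = 10% the inflation is zero. A reader might infer that the plan's true error rate is far above 0.05. The documents do not support that; they show only that 0.042 is not assured.

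Second, half is a planning estimate and, in section 8, a ceiling. That also stands, which is why the table shows 15 and 10. A reader might further suppose that many patients start goserelin at entry. No proportion is given, and one eligible pre-menopausal group has already had ovarian suppression with an aromatase inhibitor, so some may be continuing.

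Third, response is an early-efficacy question in a phase I trial, and no single-arm comparison with a historical rate can credit one component causally. This limits the weight of the point. The plan nevertheless states a null, an alpha, a power and a rejection rule, and words the aim as improvement over tamoxifen alone.

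Fourth, a reader might take the patients not on goserelin as a clean test of ribociclib. They are not:
- Goserelin use nearly coincides with menopausal status, and eligibility rules on prior therapy differ between the groups (section 4, parts B and C).
- The stratum admits patients who were unwilling to take, unsuited to or intolerant of an aromatase inhibitor, so the 10% rate after inhibitor failure may not apply.
- Escalation patients may have bone-only disease, so fewer than 20 may be assessable for response.

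**Conclusion.** The point holds as one of interpretation and labelling. P0 is set for tamoxifen alone, about 20 of 40 patients are expected to receive goserelin as well, and one pooled test is planned with no split. Rejecting P ≤ 0.10 would say that the treated mix responds at more than 10%; it would not say that ribociclib is the reason.

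With ribociclib inert, the probability of a positive result runs from 0.042 (no goserelin contribution) to 0.40 (20 patients at an assumed 25%), or to 0.17 if only 10 receive goserelin. These figures assume 10% in all other patients and independent responses. The documents do not say where in that range the truth lies. Given the secondary, early-phase role of response, this should be corrected before analysis but does not invalidate the trial.

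**What to change.** 1. Word the pooled conclusion as the response rate of ribociclib plus tamoxifen, with goserelin in pre- and peri-menopausal women, and drop the claim of improvement over tamoxifen alone.
2. Correct the P0 label in section 10.2, and the matching objective in the Synopsis, so that standard care is not equated with tamoxifen alone for all patients. Reconcile the Synopsis and section 2 on whether goserelin is part of the study.
3. Pre-specify confirmed response with exact confidence intervals by menopausal status and goserelin use, as descriptive only. Do not present the no-goserelin stratum as a test of ribociclib.
4. Record goserelin use and whether it was started at entry or was continuing. The calendar in section 8.5 collects menopausal status at baseline and on day 1 of each cycle but has no goserelin row, so it cannot be assumed that this item is already captured.

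Cost: wording, one descriptive table and possibly one added data item. Treatment and enrolment are unchanged. The downside is a narrower pooled claim and small strata with wide intervals.

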Patient Population:

Patients with estrogen and/or progesterone receptor positive, HER2-negative advanced (metastatic) breast cancer that are in one of the following populations

Pre-menopausal Women:

- A. Pre-menopausal women who received adjuvant Aromatase Inhibitor and Ovarian Suppression (AI + OS) in the adjuvant setting and completed at least 12 months of hormonal therapy.
- B. Pre-menopausal women who have never been treated with endocrine therapy with de-novo metastatic disease.
- C. Pre-menopausal women who have not received Tamoxifen in the metastatic setting, but have received up to two lines of chemotherapy for dose expansion and up to three lines for dose escalation.

Post-Menopausal Women or Men

- D. Post-menopausal women or men who have progressed on first-line or second-line therapy with an aromatase inhibitor
- E. Post-menopausal women or men who have recurred while on or after completion of adjuvant treatment with aromatase inhibitors (they have completed at least one year of adjuvant AI in the adjuvant setting before progression on AI).
- F. Post-menopausal women or men who are not considered candidates for treatment with an aromatase inhibitor by their oncologist, refused AI, or intolerant to AI
- G. Post-menopausal women or men who have been treated with up to two lines of chemotherapy for dose expansion and up to three lines for dose escalation in the metastatic setting.

Total number of patients: 40

Number of Centers: 1 (will be adjusted, increased if accrual goals are not met).

Sample Size Justification (will be updated by statistician):

For a total of **40 subjects**, about 9-12 will be accrued during phase 1 portion and **about 30 patients for the phase 1b expansion.**

Part 1: phase 1 portion:

We will evaluate the first 9-12 patients in the phase I portion for safety.
The Primary objective is safety.

Part II: phase Ib expansion:

For the phase one expansion we will include pre- menopausal women, post-menopausal women, and men evaluated as one group. We will further evaluate both a three weeks on and one week off cohort (i.e. once daily for 21 consecutive days followed by a 7-day planned break) and a *continuous dose cohort* of ribociclib administered daily (QD) without a break in each cycle. Tamoxifen will be administered daily per standard of care in both cohorts.

The **primary objective** in the phase I study is to confirm safety, tolerability, confirm DLT, and determine the RP2D of Ribociclib with Tamoxifen

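### Section 10.2 names Fisher's Exact test for a one-sample comparison that rests on the exact binomial, and its fixed cut-off of 8 does not hold the 5% level from N = 42

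*Combined protocol and SAP*

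**What the plan says.** Section 10.2 sets up the efficacy evaluation as a one-arm design: "We obtained our statistical power and required sample size as a single-arm prospective study". The question is whether the response proportion "is less than or equal to 0.100 or greater than or equal to 0.25", at "one-sided significance level 0.05 and power 0.80 as below". The 10% is a historical figure. The synopsis says "We know that the expected RR for Tamoxifen after failure of first line AI is about 10" per cent, and gives no numbers of patients or responders behind it.

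The table in 10.2 gives N = 40, a cut-off of 8, actual alpha 0.042 and actual beta 0.182. The sentence below it says that, when the cut-off is reached, "P0 is rejected based on Fisher's Exact test", citing references 34 and 35. By their titles these are exact single-stage phase II sample size tables and a one-sample phase II testing procedure.

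The closing paragraph of 10.2 requires 6 escalation and 30 expansion patients, 36 in total, and attaches a threshold of 8 responses and an actual error rate of 0.045 to that total. It then says "The null hypothesis will be rejected if 8 or more responses are observed in 40 patients", with type I error 0.045 and power 0.818.

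Other parts of the plan give other totals. The synopsis states 40 patients overall, of whom "about 9-12 will be accrued during phase 1 portion" and about 30 in the expansion. The dose table in the synopsis and Table 8-1 allow 3 to 6 patients at each of three levels, plus two expansion cohorts of 15. Section 10.2 pools escalation and expansion patients for analysis.

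**The concern.** There are two separate faults in one short section.

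The first is the name of the test. Fisher's Exact test compares two observed proportions. With one arm and a fixed 10% there is no second row in the table, so the test as named cannot be run on the data the trial will collect. This is the only powered test in the plan, so the analysis section should name one that can be carried out.

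The second is that the cut-off is a fixed count while the sample size is not settled. An exact binomial cut-off belongs to a particular N. If more patients are pooled than the cut-off was derived for, the same count is easier to reach by chance and the stated 5% level is lost. If fewer are pooled, the stated power is lost. No rule for resetting the cut-off is written.

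**Working it through.** **Inputs.** From 10.2: P0 = 0.10, P1 = 0.25, one-sided alpha 0.05, target power 0.80, cut-off 8. Sample sizes:

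- 10.2, text: 6 + 30 = 36.
- 10.2, table and final rule, and the synopsis total: 40.
- Synopsis, sample size justification: 9 to 12 plus about 30 = 39 to 42.
- Dose tables: 3 × (3 to 6) = 9 to 18, plus 15 + 15 = 30, giving 39 to 48.

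**Formula.** For cut-off c, P(X ≥ c | N, p) is the sum over x = c to N of C(N, x) p^x (1 − p)^(N − x). It gives the type I error at p = 0.10 and the power at p = 0.25.

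**Step 1: reproduce the plan's figures at N = 40.**

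- P(X ≥ 8 | 40, 0.10) = 0.0419, the table's 0.042.
- P(X ≥ 8 | 40, 0.25) = 0.8180, so beta = 1 − 0.8180 = 0.182, as tabulated.
- P(X ≥ 7 | 40, 0.10) = 0.0995, so 8 is the smallest count that meets 0.05.

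The design is therefore the one-sample exact binomial. The 0.045 in the text does not reproduce: the exact value is 0.0419 at N = 40 and 0.0235 at N = 36.

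**Step 2: could Fisher's test have produced the cut-off of 8?** It can be computed only if a control group is assumed. The documents give none, so the control sizes below are assumptions, each with exactly 10% responders.

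| Assumed controls | One-sided p for 8/40 | Smallest significant count of 40 |
|---|---|---|
| 40 | 0.174 | 11 |
| 100 | 0.096 | 10 |
| 400 | 0.055 | 9 |
| 4000 | 0.043 | 8 |

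Of these sizes only the largest gives 8, where Fisher's test approaches the one-sample binomial. It is not the source of the rule.

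**Step 3: hold the cut-off at 8 and vary N.**

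| N | Type I error, cut-off 8 | Power, cut-off 8 | Smallest valid cut-off | Its type I error | Its power |
|---|---|---|---|---|---|
| 36 | 0.0235 | 0.710 | 8 | 0.0235 | 0.710 |
| 39 | 0.0366 | 0.794 | 8 | 0.0366 | 0.794 |
| 40 | 0.0419 | 0.818 | 8 | 0.0419 | 0.818 |
| 41 | 0.0477 | 0.839 | 8 | 0.0477 | 0.839 |
| 42 | 0.0539 | 0.859 | 9 | 0.0211 | 0.757 |
| 45 | 0.0757 | 0.906 | 9 | 0.0320 | 0.827 |
| 48 | 0.1021 | 0.939 | 9 | 0.0463 | 0.881 |

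The fixed count of 8 is valid for N = 36 to 41 and exceeds 0.05 from N = 42. At N = 36 it is valid, but its power is 0.710, not the 0.80 target or the quoted 0.818.

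**The case against.** The plan's authors could fairly say that the intended test is easy to recover. The section describes a single arm, states a numerical threshold, and cites two one-sample phase II references. The table reproduces exactly, and no control counts exist that could lead an analyst elsewhere. Response is also a secondary, early-efficacy aim in a study whose primary objective is safety. All of this stands, and it limits the weight of the point.

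Three stronger readings are tempting, and the documents do not support them.

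- *That no valid rule exists unless N is exactly 40.* The count of 8 holds the 5% level at every N from 36 to 41, and 10.2 also states it directly after the total of 36.
- *That naming Fisher's test costs most of the power.* Against an invented 4/40 control group, 11 responses would be needed and the chance of reaching 11 at a true rate of 25% is 0.42. That figure depends wholly on a comparator the plan does not contain. With 4000 assumed controls the cut-off is 8 and the power is 0.82 again. An analyst following the written count would run no such comparison.
- *That the misnaming inflates the type I error.* It does not. The inflation comes from a fixed cut-off combined with an unsettled N, and renaming the test alone would leave it unchanged.

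It is also fair to say that N = 48 would require all three escalation levels to expand to six and would exceed the stated total of 40. Within the synopsis range of 39 to 42 only N = 42 breaches 0.05, by about 0.004. The larger excesses are reachable under the cohort tables, but they are not the expected case.

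**Conclusion.** The point holds in two parts. First, the named test is wrong: Fisher's Exact test cannot be applied to one arm against a fixed 10%, and the plan's cut-off, alpha and power are those of the one-sample exact binomial. The consequence is a wrong label. At N = 40 the decision rule, type I error (0.042) and power (0.818) all stand.

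Second, and independently, the fixed cut-off of 8 does not suit every sample size that the plan's own counts allow. The type I error is 0.054 at N = 42, 0.076 at 45 and 0.102 at 48. At N = 36, the total that 10.2 itself says is required, the level is kept but the power is 0.71.

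These figures assume that every pooled patient counts in the denominator and that all share one response rate, as the single-arm calculation in 10.2 does. The text's type I error of 0.045 is an error at either of the section's two totals.

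**What to change.** In Section 10.2:

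1. Replace Fisher's Exact test with the one-sample exact binomial test of P ≤ 0.10, one-sided 0.05.
2. State that the cut-off is set by the number of patients analysed for response: 8 for N = 36 to 41 and 9 for N = 42 to 48. Say which patients are in that number, since escalation and expansion patients are pooled.
3. Reconcile the totals of 36 and 40, align them with the synopsis and Table 8-1, and restate the power that applies: 0.71 at 36, 0.82 at 40, 0.76 at 42 with cut-off 9.
4. Correct the type I error in the text from 0.045 to 0.042 for N = 40.

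This is an edit to the text of one section plus alignment of the patient counts. Treatment, assessments and data collection do not change. The cost is that the plan must admit power below 0.80 at some sample sizes, notably 36 and 42. If the sponsor does not accept that, it must commit to an N at which the target is met, such as the 40 already stated.
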